4.2.1 Primary Endpoint – Time to First COPDCompEx Event

4.2.1.1 Definition

The COPDCompEx is a composite endpoint developed to estimate the magnitude of treatment effect on COPD exacerbations over 52 weeks, in a 12-week study. It incorporates change in symptoms, reliever use and PEF obtained from daily diary, with confirmed exacerbations and/or study drop-outs.

The definition of the event is one of the following criteria:

- Moderate or severe exacerbations: episodes leading to one or more of the following: hospitalization, emergency room visit, an episode of pneumonia, treatment with OCS or corticosteroid depot injection, or treatment with antibiotics.
- *Diary events*: defined by threshold and slope criteria using the following diary and home spirometry variables: overall symptom rating, reliever medication use, and change in PEF.
- *Study dropouts*: early treatment discontinuation due to lack of efficacy.

The COPDCompEx definition and derivation are detailed in AZ Business Rules.

Time to first COPDCompEx event is defined as time elapsed from the start of study treatment to the occurrence of the first COPDCompEx event.

4.2.1.2 Derivations

Time to first COPDCompEx event will be calculated as:

Time to first COPDCompEx event (days) = [Start date of first event/censoring – date of the first dose of study intervention+ 1].

For participants who do not experience an on-treatment COPDCompEx event, date of censoring will be the last dose date or last date of eDiary recording – whichever is earlier.

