Provision and training on use of spirometer and e-Diary Assess adherence to the		X							Compliance to COPDCompEx (e-Diary) should be assessed at each study visit. Participants must demonstrate a compliance of	8.2.3, 8.2.6
completion of e-Diary entries and home device use			X	X	X	X	X		at least 70% during the 14 days preceding SV3 to be eligible for randomisation.	

e-Diary and PEF (2 × daily recording) ^c D=distribute, R=Return		D	-		-		R		During the study treatment period, daily e-Diary compliance is critical for overall symptom rating, reliever medication use, and change in PEF. The investigator/authorised delegate should check the participant's adherence to the daily e-Diary at each visit and remotely at any time during the study. If it drops below 80% to 85%, sites should take steps to ask the participant about the reason and to encourage the participant to regularly complete the e-Diary. If compliance does not improve, or there is reason why the assessments cannot be completed (eg. temporary discontinuation or hospitalisation), the AstraZeneca study team should be contacted for discussion. Participants who fail to meet compliance rate may be rescreened once only. The baseline for COPDCompEx will be estimated during the period between SV2 and SV3. Participants should bring their spirometer and the device with the e-Diary on to all on-site visits. e-Diary and PEF will be recorded up until the day of SV7 or EDV.	
Cough VAS assessment				→	-	→	→		Cough VAS assessment will be recorded up until the day of SV7 or EDV.	8.2.4
CAT			X		X		X			8.2.5
EXACT			X		X		X			0.2.4
BCSS (daily)			-	→	→	-			BCSS (daily) assessment will be recorded up until the day of SV7 or EDV.	8.2.4
Serum chemistry	X		X	X	X		X	X		8.3.4
T3, T4, TSH	X		X		X		X	X		
Systemic biomarkers of			X		X		X			8.8

Procedure	(up to	ening 28 days Day 1)	Intervention Period					Follow-up Period	Notes	Details in protocol section or appendix
Visit	SV1	SV2	SV3	SV4	SV5	SV6 (VV) ^a	SV7/ EDV ^b	SV8	Study procedures should take place prior to dosing, unless specified otherwise.	
Weeks	-4	-2	1	4	12	18	24	+ 2 post- SV7/EDV	Participants discontinuing study intervention before SV7 should attend the site for SV7 assessments as soon as possible as an EDV. See Section 7.1.4 for details of study end when the last participant has completed 12 weeks of treatment. Visits SV2, SV4, SV7/EDV, and SV8 are visits with a reduced number of assessments. SV6 is a virtual visit.	

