4.2.1.3 Handling of Dropouts and Missing Data

The "while on treatment" strategy will be used for the primary estimand: if an intercurrent event occurs before first COPDCompEx event, the patient will be censored at the time of intercurrent event.

For participants who do not experience an on-treatment COPDCompEx event,

• If intercurrent event is earlier than date of last dose or the last eDiary date, the participant will be censored at intercurrent event date.

• If the intercurrent event is after the last eDiary date, but earlier than date of last dose, participants who do not experience an on-treatment COPDCompEx event, date of censoring will be last day of eDiary recording.

Intercurrent events are events occurring after treatment initiation (eg, premature treatment discontinuation, switching treatment, terminal events such as death) that affect either the measurement or interpretation of the summary measure (eg, hazard ratio) associated with the clinical question of interest. This study contains 2 intercurrent events:

- 1. Treatment discontinuation (with the following reasons: SAE, death not due to exacerbation, COVID-19, pneumonia, other).
- 2. Prohibited medication.

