4.2.1.4 Primary Analysis of Primary Endpoint

Kaplan-Meier curves, region-stratified logrank test and region stratified Cox proportional hazard (PH) model results, will be provided for time to first COPDCompEx event as specified in Section 3.4.1.

The evidence of efficacy requires a two-sided region-stratified logrank test p-value ≤ 0.10 .

Kaplan-Meier curve estimates will be provided with a 90% CI.

Survival probabilities will be presented as survival curves estimated using the Kaplan-Meier method.

Diagnostic plot (log-log) will be presented to assess proportional hazard assumption.

The hazard ratio estimate from the Cox PH model will be provided with a 90% CI.

COPDCompEx data will be listed.

The analyses will be focused on the FAS population, including only those subjects with post-baseline eDiary data.

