4.2.2.2 Derivations

Time to first moderate or severe COPD exacerbation event will be calculated as:

Time to first moderate or severe COPD exacerbation event (days) = [Start date of first event/censoring – date of the first dose of study intervention+1].

The date of first moderate or severe COPD exacerbation event will be the first start date of a moderate or severe COPD exacerbation event, i.e. the earliest of the exacerbation which meets the definition of moderate or severe COPD exacerbation.

For participants who do not experience an on-treatment moderate or severe COPD exacerbation event, date of censoring will be the date of last dose.

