4.2.10 Tertiary/Exploratory Endpoint – Annualised rate of COPDCompEx Event

4.2.10.1 Definition

The COPDCompEx definition and derivation are detailed in AZ Business Rules.

Events regardless of what type (i.e., acute worsening or exacerbation) must be separated by at least 14 days in order to count as separate events (i.e., there must be at least 14 days during which no criteria for events are fulfilled).

The time during the event and the 14 days after each event will not be considered when defining time at risk for the COPDCompEx event rate. Time at risk (days) will be defined as

[Date of last dose of study intervention – date of the first dose of study intervention] + 2 – recovery time.

Where recovery time is defined as:

$$\sum_{i=1}^{k} [min(i^{th} event end date + 14, date of last dose of study intervention) - i^{th} event start date + 1]$$

4.2.10.2 **Derivations**

Annualised rate of COPDCompEx events, based on the period from baseline to last dose, will be calculated as:

Annualised rate of COPDCompEx events

Total number of COPDCompEx events

Total number of COPDCompEx events

(Date of last dose of IP – Date of the first dose of IP – recovery time + 2)/365.25

For participants who do not experience an on-treatment COPDCompEx event, date of censoring will be the last dose date or last date of eDiary recording whichever is earlier.

For CompEx analyses, only on-treatment events (i.e., events occurring from randomisation up to and including the last dose day) will be considered.

4.2.10.3 **Handling of Dropouts**

The "while on treatment" strategy, same as defined in section 4.2.1.3.

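### The primary analysis censors event-free participants at the last eDiary date but counts exacerbations up to last dose, so follow-up after the diary stops depends on the later outcome

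*SAP*

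**What the plan says.** **Censoring side.** SAP 4.2.1.2 sets the censoring date only for participants who have no on-treatment event: "date of censoring will be the last dose date or last date of eDiary recording", taking the earlier. SAP 4.2.1.3 keeps that condition. Even when an intercurrent event falls after the last diary entry but before last dose, the "date of censoring will be last day of eDiary recording".

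**Event side.** Two of the components in SAP 4.2.1.1 matter here. Diary events are "defined by threshold and slope criteria using the following diary and home spirometry variables". The other component is "Moderate or severe exacerbations: episodes leading to one or more of the following: hospitalization, emergency room visit, an episode of pneumonia", or steroid or antibiotic treatment; none of these needs diary data. SAP 4.2.10.2 sits in the event-rate section but is worded for CompEx analyses generally: "only on-treatment events (i.e., events occurring from randomisation up to and including the last dose day) will be considered". The on-treatment period in SAP 3.3.2 does not mention the eDiary either.

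**Observation after the diary stops.** The Schedule of Activities assesses exacerbations at SV3 to SV7. For the exacerbation endpoint, SAP 4.2.2.2 says the "date of censoring will be the date of last dose".

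**Planned coverage and checks.** Under Protocol 1.3, "e-Diary and PEF will be recorded up until the day of SV7 or EDV". The primary analysis uses the FAS, "including only those subjects with post-baseline eDiary data" (SAP 4.2.1.4). SAP 4.2.1.5 plans no sensitivity analysis, and the treatment-policy analysis in 4.2.1.6 changes only the handling of intercurrent events.

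**The concern.** Kaplan-Meier and Cox methods require that being at risk on a given day depends only on what has happened up to that day. Here, once the diary has stopped, it depends on what happens later: a participant who goes on to have an exacerbation stays in the risk set, and one who does not is taken out retrospectively.

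The post-diary period thus contributes events without the event-free time that belongs with them. The Kaplan-Meier estimates reported at Weeks 4, 12, 18 and 24 would be too high in whichever arms have diary gaps. If one arm has more early stopping, its hazard is inflated more and the primary hazard ratio moves. Nothing in the planned analyses would reveal this.

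**Working it through.** **1. Planning figures, reproduced.** Inputs from SAP 3.3: hazard ratio 0.70, two-sided 10% level, 80% power, 1:1 allocation, placebo 24-week risk 55%.

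- Events = 4(z₀.₉₅ + z₀.₈₀)² / (ln 0.70)² = 4 × (1.6449 + 0.8416)² / 0.35667² = 194.4, against 194 stated.
- Participants, if all are followed for 24 weeks: 194 / (0.55 + 1 − 0.45^0.70) = 194 / 0.9782 = 198.3 per arm, against 203 stated.

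The censoring rule does not alter this calculation.

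**2. The mechanism.** Take two participants whose diaries stop at Week 8 and who take drug to Week 24. One has an exacerbation at Week 16; the other has none.

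- As written: the first contributes 16 − 8 = 8 weeks and 1 event after Week 8. The second contributes nothing. Rate: 1 event per 8 person-weeks.
- Both followed to event or last dose: 8 + (24 − 8) = 24 person-weeks and 1 event. Rate: 1 per 24.
- Both stopped at Week 8: no time and no event after Week 8.

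Either of the last two is coherent. The first is not.

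**3. Size, by simulation.** Two inputs are assumptions because the documents do not give them: the share of participants whose diary stops before last dose, and the share of the event hazard due to exacerbations. The runs below use constant hazards, 200,000 per arm, true hazard ratio 0.70, follow-up uniform over 12-24 weeks, a 40% exacerbation share, and diary stopping unrelated to event risk. Kaplan-Meier risk is read at Week 23.5, where the true placebo value is 1 − 0.45^(23.5/24) = 54.2%. Compare within rows; the hazard ratios carry simulation noise of about 0.005.

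| Early stop, placebo / active | Placebo risk, as written | Placebo risk, common end | HR, as written | HR, common end |
|---|---|---|---|---|
| 0 / 0 | 54.2% | 54.2% | 0.705 | 0.705 |
| 5% / 5% | 54.4% | 54.1% | 0.696 | 0.696 |
| 10% / 10% | 54.9% | 54.1% | 0.704 | 0.703 |
| 30% / 30% | 56.9% | 54.2% | 0.698 | 0.696 |
| 10% / 20% | 54.8% | 54.1% | 0.718 | 0.706 |
| 20% / 10% | 55.9% | 54.2% | 0.689 | 0.698 |

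Over 5-30% stopping and 30-50% exacerbation share, the excess placebo risk is about 0.3-3 points. A 10-point difference in stopping gives a hazard ratio of about 0.69-0.72; a 20-point difference gives up to about 0.74.

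**4. Against the trial's precision.** SE(ln HR) = 2/√194 = 0.144, so the 90% interval around 0.70 is about 0.55-0.89. A shift to 0.72 is ln(0.72/0.70)/0.144 = 0.2 SE; to 0.69, 0.1 SE; to 0.74, 0.4 SE. At 203 per arm with a 50% exacerbation share (4,000 runs), rejection at a true hazard ratio of 0.70 was 71% as written against 75% with a common end for 10%/20% stopping, and 65% against 74% for 10%/30%. With a true hazard ratio of 1, rejection stayed at 9.7-10.9%.

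**5. Checking the remedy.** A strict cut at the last eDiary date discards exacerbations that themselves end the diary. If 10% of exacerbations are preceded by a permanent diary stop (an assumption), that cut gives a placebo risk of about 53-54%, too low. A common end with a short allowance after the last eDiary date returned about 54-55% and a hazard ratio of about 0.69-0.71.

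**The case against.** The strongest reply is that gaps should be uncommon and their effect small. The diary runs to SV7 or EDV. Entry requires 70% compliance (Protocol 5.1), and sites act when adherence falls below 80% to 85% (Protocol 8.2.6). Missed days matter only if no later entry exists. At 2-5% stopping in both arms, the excess risk is 0.15-0.4 points with the hazard ratio at 0.70. Efficacy is judged by the logrank test, not by absolute risk. All of this stands, and it limits the size. It does not remove the inconsistency: SAP 4.2.1.3 has a rule for a diary that ends before last dose, so the plan itself expects gaps.

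Two further points also stand. COPDCompEx derivation is deferred to the sponsor's Business Rules, which might restrict post-diary events; the SAP does not say that they do. And diary cessation is not one of the two intercurrent events, so simply cutting at the last diary date would discard confirmed on-treatment exacerbations. The schedule's own e-Diary note names hospitalisation as a reason diary assessments may not be completed.

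A reader might infer that the primary hazard ratio is biased or the type I error inflated. The documents do not support that. The hazard ratio moves only with unequal stopping, nothing in the documents indicates a difference between blinded arms, and simulated rejection under no effect stayed near 10%.

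**Conclusion.** The inconsistency holds on the SAP text: events and censoring have different follow-up ends, and the time between them counts only for those who have an event. The consequence is conditional. With diary gaps, Kaplan-Meier risk is overstated, by about 0.3-3 points on 55% under the assumed ranges. The hazard ratio is unaffected by equal stopping and moves to about 0.69-0.72 with a 10-point imbalance; more stopping on active pulls it toward 1, more on placebo pulls it away.

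It would go too far to say that reported risks will be overstated in this trial: with no gap the bias is zero, and the stopping rate is not given. The simulations also assume that diary stopping is unrelated to event risk and that exacerbations are fully captured after the diary stops. Protocol 8.2.6 collects steroid, antibiotic and hospitalisation reports partly through the diary, so capture may be incomplete. This is a modest defect in the primary endpoint's derivation, worth correcting before unblinding because correction is cheap.

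**What to change.** - In SAP 4.2.1.2 and 4.2.1.3, define one follow-up end for every participant: the earliest of last dose, intercurrent event, and last eDiary date plus a short fixed allowance (for example 7 days). A first event counts only if it starts by that date; event-free participants are censored at that same date. The allowance keeps an exacerbation that itself stops the diary.
- In 4.2.1.6, make the event and censoring windows of the treatment-policy analysis match as well. As written, it keeps the same asymmetry.
- In 4.2.1.5, add a sensitivity analysis that follows everyone to last dose for exacerbations.
- Report early diary stopping by arm, and confirm that the Business Rules agree with the chosen window.

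**Cost.** A few sentences and one additional analysis. Assuming 5-30% early stopping, at most about 1-8% of first events, those starting after the allowance, leave the primary analysis. They still count in the exacerbation endpoint (SAP 4.2.2.2). The change removes outcome-dependent follow-up; it does not correct for participants who stop the diary because they are getting worse.

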4.2.1.3 Handling of Dropouts and Missing Data

The "while on treatment" strategy will be used for the primary estimand: if an intercurrent event occurs before first COPDCompEx event, the patient will be censored at the time of intercurrent event.

For participants who do not experience an on-treatment COPDCompEx event,

• If intercurrent event is earlier than date of last dose or the last eDiary date, the participant will be censored at intercurrent event date.

• If the intercurrent event is after the last eDiary date, but earlier than date of last dose, participants who do not experience an on-treatment COPDCompEx event, date of censoring will be last day of eDiary recording.

Intercurrent events are events occurring after treatment initiation (eg, premature treatment discontinuation, switching treatment, terminal events such as death) that affect either the measurement or interpretation of the summary measure (eg, hazard ratio) associated with the clinical question of interest. This study contains 2 intercurrent events:

- 1. Treatment discontinuation (with the following reasons: SAE, death not due to exacerbation, COVID-19, pneumonia, other).
- 2. Prohibited medication.

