3.3.2 Periods

Pre-treatment period

The pre-treatment period starts at the date of signed informed consent and ends before the date and timepoint of first dose of Investigational Product (IP).

On-treatment period

The on-treatment period will be calculated from the date and timepoint (as in time of day) of the first dose of IP to the earliest of date of last dose, date of withdrawal of consent or date of death. If withdrawal of consent or death did not occur, it will be calculated from the time of the first dose of IP to the earliest of date of last dose of study drug or the last study visit. If the timepoint of first dose of IP is missing, only the day of first dose of IP will be used.

Follow-up period

The follow-up period will be calculated from the date of last dose of IP + 1 day to the date of last visit.

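### SAP 4.2.1.3: the *or* in the first censoring bullet gives the primary endpoint a conflicting or too-late censoring date in two orderings of intercurrent event, last dose and last eDiary date

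*SAP*

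**What the plan says.** Four statements in the SAP bear on the censoring date of the primary endpoint.

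- Section 4.2.1.2 covers event-free participants in general: "date of censoring will be the last dose date or last date of eDiary recording – whichever is earlier".
- Section 4.2.1.3 opens with the while-on-treatment strategy: "if an intercurrent event occurs before first COPDCompEx event, the patient will be censored at the time of intercurrent event".
- The same section then gives two bullets under one lead-in, "For participants who do not experience an on-treatment COPDCompEx event". The first reads: "If intercurrent event is earlier than date of last dose or the last eDiary date, the participant will be censored at intercurrent event date".
- The second bullet begins "If the intercurrent event is after the last eDiary date, but earlier than date of last dose" and concludes that the "date of censoring will be last day of eDiary recording".

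Two further places define when an event can count. Section 3.3.2 runs the on-treatment period from first dose "to the earliest of date of last dose, date of withdrawal of consent or date of death". Section 4.2.10, under the derivation of the COPDCompEx rate, says that for CompEx analyses "only on-treatment events (i.e., events occurring from randomisation up to and including the last dose day) will be considered".

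**The concern.** Bullet 1 is triggered when the intercurrent event precedes either date. For its result to be the earliest of the three dates, the event would have to precede both. Section 4.2.1.2 makes its choice between two dates explicit by saying that the earlier applies; bullet 1 names the same two dates without those words.

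This is the censoring rule behind the region-stratified logrank test on which evidence of efficacy rests (SAP 4.2.1.4), and SAP 4.2.1.5 plans no sensitivity analysis of the primary endpoint. Two programmers working from the text could derive different censoring dates for the same participant. One of those dates can lie outside the on-treatment window.

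**Working it through.** The rule rests on no numerical figure, so there is none to reproduce. The check is one of logic.

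**Inputs.** Let I be the intercurrent event date, L the last dose date and E the last eDiary date, for a participant with no on-treatment event.

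- Bullet 1 (4.2.1.3): if I < L or I < E, censor at I.
- Bullet 2 (4.2.1.3): if E < I < L, censor at E.
- Default (4.2.1.2): censor at min(L, E).

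The bullets are taken to override the default when triggered. Otherwise the default would cancel bullet 1 even when the intercurrent event comes first, which cannot be meant.

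**All orderings.** Three dates can be ordered in 13 ways: 6 strict and 7 with ties.

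- Five orderings have I first, alone or tied with one other date (I<L<E, I<E<L, I<L=E, I=L<E, I=E<L). Bullet 1 gives I, which is the earliest date.
- Six have I earlier than neither L nor E (I=L=E, L=E<I, L<E<I, E<L<I, L<I=E, E<I=L). No bullet applies, and the default gives the earliest date.
- Two remain, and both fail. The days below are invented for illustration.

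| Ordering | Example | Bullet 1 | Bullet 2 | 4.2.1.2 | Earliest of three |
|---|---|---|---|---|---|
| E < I < L | E=60, I=75, L=84 | 75 | 60 | 60 | 60 |
| L < I < E | L=70, I=74, E=80 | 74 | not triggered | 70 | 70 |

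In the first ordering the candidate dates differ by 75 − 60 = 15 days. Every such record also meets bullet 1, because I < L, so bullet 2 never applies alone. In the second, bullet 1 censors 74 − 70 = 4 days after the last dose. Events count only up to and including the last dose day, so days 71 to 74 are at-risk time in which none can be counted.

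**Can both orderings occur?** Yes.

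- E < I < L needs a diary that lapses for good, then prohibited medication while dosing continues. Prohibited medication is one of the two listed intercurrent events.
- L < I < E needs prohibited medication to start, or a discontinuation to be dated, after the last dose while the diary continues. The protocol's Schedule of Activities keeps the diary running to SV7 or the early discontinuation visit, so it can outlast dosing. The SAP does not say whether a discontinuation is dated at the last dose or at the later decision.

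**After the correction.** With bullet 1 changed to I < L and I < E, and 4.2.1.2 as the default, all 13 orderings give a single date equal to min(I, L, E). The two examples give day 60 and day 70.

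**Reach.** Section 4.2.10.3 adopts 4.2.1.3 for the COPDCompEx rate, so the wording carries over by reference. The time to first moderate or severe exacerbation (4.2.2.3) uses only the last dose and is not affected.

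**The case against.** The best defence is that the intent is recoverable. Bullet 2 exists only for E < I < L and names the date; 4.2.1.2 gives the same one, and bullet 1 echoes the pair of dates that 4.2.1.2 resolves by taking the earlier. For that ordering the defence largely stands: a careful programmer would probably arrive at the last eDiary date. What remains is that two bullets for the same participants conflict with no stated priority, and that the strategy sentence opening 4.2.1.3 favours bullet 1.

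The defence is weaker for L < I < E. Bullet 2 does not apply there, so treating it as the specific exception leaves bullet 1 in force. It is fair to say that the SAP never states that a discontinuation is dated after the last dose, so that route rests on an assumption. Prohibited medication started after the last dose reaches the same ordering without it.

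A reader might infer three stronger things that the documents do not support.

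- That the extra days favour or penalise the arm with more discontinuations. In E < I < L dosing continues after the intercurrent event, so permanent discontinuation is not the cause, and nothing shows that use of prohibited medication differs by arm. In L < I < E the documents give no counts by arm.
- That follow-up after the diary lapses is unobservable. Only diary-defined events are lost. Exacerbations and discontinuations for lack of efficacy are also components of the endpoint (4.2.1.1) and can still be recorded.
- That the rule cannot be programmed. It can be, once the evident intent is adopted; the text just does not state it.

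**Conclusion.** The point holds as a wording error in the primary censoring rule. Taken literally, bullet 1 contradicts bullet 2 and 4.2.1.2 in one ordering, and in another it censors after the on-treatment window has closed.

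For an affected participant the discrepancy is I − E or I − L days. How many participants are affected, and by how much, is not given in the documents and cannot be derived from them. The effect on the hazard ratio therefore cannot be sized. It is probably small, because each ordering needs an uncommon sequence of dates in a participant who also has no on-treatment event. This conclusion assumes that the bullets take precedence over 4.2.1.2 when triggered.

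**What to change.** In bullet 1 of SAP 4.2.1.3, require the intercurrent event to be earlier than both the date of last dose and the last eDiary date, and state that 4.2.1.2 applies when neither bullet is met. Equivalently, replace the two bullets with one rule for the same event-free participants: *censor at the earliest of intercurrent event date, last dose date and last eDiary date*. The opening strategy sentence can stay. Section 4.2.10.2 needs no separate rewrite, because 4.2.10.3 already refers back to 4.2.1.3.

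The cost is one clause in the SAP and a check of one line in the derivation program. If made before unblinding, it removes a choice that would otherwise be left to the programmer. Where the literal reading had been programmed, some participants would have slightly shorter follow-up.
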